7.3.4 Adult Household Contact Viral Acquisition

The principal analysis of adult household contact viral acquisition will be restricted to households with at least two adults for which no other adult besides the index study subject is positive for COVID-19 at baseline. We will evaluate the effect of the hydroxychloroquine intervention on the risk of adult household viral acquisition by applying a Cochran-Mantel-Haenszel test stratifying by the randomization age categories and total number of adults within the household (with this total number being regardless of whether or not the adults contributed to the study’s swab collection). Results will be presented as relative risks with 95% confidence intervals within each stratum, and then pooled across strata. A secondary analysis will assess the effect of treatment arm on household viral acquisition rates averaged across all non-index adults within the household by using a modified Poisson regression model incorporating correlation between participants in the same household, and controlling for age category and number of household members. The analyses in this paragraph will be conducted twice, once when using the principal version of the outcomes (i.e., using swabs collected from *DayR* + 1 to *DayR* + 14, inclusive) and once when using the additional exploratory versions of the outcomes (i.e., using all collected swabs from *DayR* + 1 to the Day 28 swabs, inclusive).

7.4 Exploratory Outcomes Analyses

The original protocol mentioned an analysis of viral shedding numerical measurements. Such an analysis may or may not be conducted; if conducted, the analysis will be described

elsewhere and regarded as an exploratory analysis.

7.4.1 Duration of COVID-19 attributable symptoms

As noted in Section 5.4 of this SAP, we will analyze symptom duration through *DayA15*, rather than Day 28, which is a departure from what was described in the protocol.

The duration of COVID-19-attributable symptoms will be summarized graphically using Kaplan-Meier curves, and compared between randomized groups by applying the Gehan test with stratification by the age group.

As a sensitivity analysis, the duration of symptoms will be recalculated without any restrictions for having confirmation. That is, the first asymptomatic day in the window will be regarded as the end date, even if the next available symptom assessment indicates a symptomatic day. The symptom duration analysis will be repeated on this modified version of the outcome.

7.4.2 Six-month mortality

Subjects for whom this outcome cannot be ascertained will be excluded from analysis of this exploratory outcome.

The frequency and percentage of ITT subjects known to have died by six months will be calculated, overall and by treatment arm. In addition, the estimated relative risk within each stratum will be reported along with a 95% confidence interval, and the Cochran-Mantel-Haenszel estimate of a common relative risk will be reported along with a 95% confidence interval.

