Six months after enrollment, study staff will verify subsequent hospitalizations and vital status of the participant.

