7.5 Discontinuance of HCQ

Patients may choose to discontinue HCQ for any reason, and HCQ will be discontinued if a known contraindication arises. Study procedures should otherwise continue. This is not the same as withdrawal from the study.

7.6 Withdrawal from study.

Patients may withdraw from the study at any time. Data recorded up to the time of withdrawal will be included in the study analysis.

UTAH One (Understanding Treatment And Health in the Ongoing coroNa Epidemic): A Hydrochloroquine Outpatient Study

7.7 Protocol deviations and violations.

The investigator will not implement any deviation from, or changes of the protocol without prior review and documented approval/favorable opinion from the IRB of an amendment, except where necessary to eliminate immediate hazard(s) to study subjects or research personnel,, or when the change(s) involves only logistical or administrative aspects of the trial (e.g., change of telephone number(s)). Protocol deviations will be reported to the DCC within 24 hours of the site becoming aware of the deviation. The study team will provide explanation of the deviation to the DCC. The DCC will notify the IRB of protocol deviations that have potential impact on human subjects safety or trial integrity. The investigator may implement a deviation from, or a change of, the protocol to eliminate immediate hazard(s) to trial subjects without prior IRB approval/favorable opinion. As soon as possible, the implemented deviation must be reported to the DCC, which will notify the medical monitor and the IRB.

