5.2 Methods for Withdrawals, Missing Data, and Outliers

Subjects with incomplete data for a variable needed in an analysis may, for example, be omitted from that analysis or have the last observation carried forward. Which technique is used depends on the analysis, as described later in the SAP.

Rates of missingness in the primary outcome will be compared between treatment arms for the ITT, dITT, and PP populations. If a substantial number of subjects have incomplete data for this outcome, analyses will be conducted to determine factors significantly related

to missingness. The factors assessed would include, at a minimum, assigned treatment arm and true age stratum.

When multiple imputation is employed, it will be performed separately within each treatment arm if possible (by ITT arm for analyses of the ITT population or subpopulations thereof, or, if necessary, by SAFETY arm for analyses of the SAFETY population).

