7.4.9 Additional Analyses for Time-to-event Outcomes

Kaplan-Meier incidence curves will also be created by treatment group for the following:

- Time to death
- Time to first hospitalization and death out of the hospital (as competing risks)
- Time to no symptoms and death (as competing risks)

For all but the first, the cumulative incidence curves for the composite outcome including death would be depicted along with cumulative incidence curves for death and for the other outcome overlaid on the plot.

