7.5 Safety Analyses

7.5.1 Formal Safety Outcome(s)

In addition to outcomes described earlier in this section, additional exploratory safety outcomes for this trial include:

- Mortality by 14 days
- Mortality by 28 days
- Hospital admission by 28 days

The analysis of each of these additional safety outcomes will be conducted in analogous fashion to the six-month mortality and six-month hospitalization endpoints (see Sections 7.4.2 and 7.4.3). For these exploratory outcomes, the analysis will be conducted on the ITT and SAFETY populations, with emphasis on the former.

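### SAP 7.4.2 drops participants of unknown six-month vital status but keeps every known death, which can modestly overstate mortality risk and, if loss differs by arm, shift the relative risk

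*SAP*

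**What the plan says.** SAP 7.4.2 gives one missing-data rule: "Subjects for whom this outcome cannot be ascertained will be excluded from analysis of this exploratory outcome". It continues: "The frequency and percentage of ITT subjects known to have died by six months will be calculated, overall and by treatment arm". Relative risks with 95% intervals are to be given within each stratum, and "the Cochran-Mantel-Haenszel estimate of a common relative risk will be reported along with a 95% confidence interval". No hypothesis test is specified.

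Other provisions bear on this:

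- Protocol 5.5 on follow-up: "Six months after enrollment, study staff will verify subsequent hospitalizations and vital status of the participant".
- Protocol 7.6, and the definition of withdrawal in Protocol 1.0: "Data recorded up to the time of withdrawal will be included in the study analysis".
- SAP 7.4.9: "Kaplan-Meier incidence curves will also be created by treatment group for the following". Time to death is on the list that follows, but no effect estimate or interval is attached to it.
- SAP 5.2: "Rates of missingness in the primary outcome will be compared between treatment arms for the ITT, dITT, and PP populations". No such comparison is planned for six-month mortality.
- SAP 5.4 defines mortality at 14 and 28 days. It has no definition of six-month mortality and no criterion for when status cannot be ascertained.
- SAP 7.5.1, on mortality at 14 and 28 days and 28-day hospital admission: "The analysis of each of these additional safety outcomes will be conducted in analogous fashion to the six-month mortality and six-month hospitalization endpoints".
- SAP 2.1.4 classes six-month mortality as exploratory.

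**The concern.** A death can become known on any day of follow-up. Survival counts as known only if there is information at six months. Whether a person stays in the analysis therefore depends partly on the outcome. Someone who dies in week 2 is kept. Someone seen alive at four months who then withdraws is removed, together with four months of survival.

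This goes beyond ordinary missing data, because the resulting risk can be wrong even when loss has nothing to do with prognosis. Each arm's reported mortality is at stake and, if loss differs between arms, so is the relative risk. SAP 3.3 says that the placebo is distinguishable from HCQ and that coordinators are not blinded, so unequal retention is conceivable. The plan has no by-arm check that would show it for this outcome.

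**Working it through.** **Plan's own figure.** The documents state no mortality rate, loss rate or precision for this outcome, so there is no figure to reproduce. Protocol Table 2 concerns the primary endpoint and assumes that all 400 participants are evaluable.

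**Inputs.** From the documents: about 200 participants per arm (Protocol 2.7). By assumption: true six-month mortality p = 2%; share of survivors whose status is unknown d = 10% or 20%; share of deaths that stay unknown u, varied relative to d.

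**Step 1: risk under the exclusion rule.**

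Complete-case risk = p(1 − u) / [p(1 − u) + (1 − p)(1 − d)]

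Example with d = 20% and u = 0: 0.02 / (0.02 + 0.98 × 0.80) = 0.02 / 0.804 = 2.49%, which is 1.244 times the true 2%.

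Ratio of complete-case risk to true risk:

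| d | u = 0 | u = d/2 | u = d | u = 1.5d |
|---|---|---|---|---|
| 10% | 1.109 | 1.054 | 1.000 | 0.945 |
| 20% | 1.244 | 1.122 | 1.000 | 0.877 |

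Risk is overstated only when u is below d. At u = d there is no bias, and above it the bias is downward. The ratios change little for p between 0.5% and 5%: at d = 20% and u = 0 they run from 1.248 to 1.235.

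**Step 2: which u to expect when loss is unrelated to prognosis.** This was simulated with 4,000,000 participants per scenario, p = 2%, loss at a constant rate independent of death, and deaths after loss unknown.

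| Loss by six months | Timing of deaths | Complete-case / true | Kaplan-Meier / true |
|---|---|---|---|
| 10% | spread evenly | 1.055 | 1.00 |
| 10% | first sixth of follow-up | 1.10 | 1.00 |
| 20% | spread evenly | 1.122 | 1.00 |
| 20% | first sixth of follow-up | 1.22 | 1.00 |

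Evenly spread deaths behave like u = d/2, and early deaths approach u = 0. A true 2% is thus reported as about 2.1% (2 × 1.055) to 2.4% (2 × 1.22). Kaplan-Meier on the same data recovers the true risk.

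**Step 3: relative risk when the true value is 1.** Divide the two arms' complete-case risks at p = 2%. For 10% versus 20% loss and u = 0: 2.488% / 2.217% = 1.122.

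| Loss by arm | u = 0 | u = d/2 | u = d | u = 1.5d |
|---|---|---|---|---|
| 10% / 10% | 1.00 | 1.00 | 1.00 | 1.00 |
| 5% / 10% | 1.054 | 1.028 | 1.00 | 0.971 |
| 10% / 20% | 1.122 | 1.064 | 1.00 | 0.928 |
| 5% / 25% | 1.260 | 1.134 | 1.00 | 0.858 |

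**Step 4: scale against sampling error.** At 2% mortality, 200 per arm gives 200 × 0.02 = 4 deaths per arm. The standard error of the log relative risk is √(2/4 − 2/200) = 0.70, so the 95% interval around 1 is exp(±1.96 × 0.70) = 0.25 to 3.94. With 2 deaths per arm it is 0.14 to 7.03.

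A second simulation (200,000 trials of 200 per arm, no true difference, u = 0) gave the chance that the interval excludes 1:

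| p | no loss | 10% / 20% | 5% / 25% |
|---|---|---|---|
| 2% | 1.1% | 1.2% | 2.1% |
| 5% | 3.8% | 4.7% | 7.0% |

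**The case against.** Several stronger readings are tempting, and the documents do not support them.

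- *Only people without the event are removed, so risk must be inflated.* Those removed have no known death; some may have died after contact ended. If deaths go unknown as often as survival, the bias is zero. If they go unknown more often, for example because sicker people are harder to trace, it reverses.
- *The relative risk is false.* That needs unequal loss. The documents neither report nor predict it, and equal loss leaves the ratio essentially unchanged.
- *Losing contact means exclusion.* Staff are to verify vital status at six months (Protocol 5.5), SAP 5.4 refers to a six-month chart review, and consent includes access to medical records (Protocol 4.1). The assumed 10% to 20% may be too high. Unknowns need not be nil, however: in defining 14-day hospitalization, SAP 5.4 itself foresees withdrawals that bar chart review.
- *This is the key safety outcome.* The SAP calls it exploratory, and its safety list (SAP 2.1.5) names 28-day mortality instead.
- *The same flaw affects mortality at 14 and 28 days.* SAP 7.5.1 asks for an analogous analysis, so carrying over the exclusion is an inference, and over such short follow-up any effect should be small.
- *The rule contradicts Protocol 7.6.* That section keeps data up to withdrawal in the study's analysis but does not promise them a place in every endpoint's denominator. The time-to-death curve can use them. The fit is poor, but it is not a contradiction.

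Two objections concern the remedy. Kaplan-Meier estimates can carry the same asymmetry if charts reveal deaths after last contact while survivors without chart entries are censored at last contact. This stands as a condition on the fix: the censoring rule must be explicit and the same in both arms. An unstratified Kaplan-Meier difference also gives up the age stratification, which is a reason to keep the stratified relative risk beside it.

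**Conclusion.** The point holds in a limited form. The exclusion is a stated method that treats known deaths and people lost while alive differently. It overstates risk when deaths are captured better than survival, the expected case if loss is unrelated to prognosis and some deaths precede loss. At an assumed 2% mortality and 10% to 20% loss, the overstatement is about 1.05 to 1.22 times. For an assumed 10% versus 20% loss, a true relative risk of 1 becomes about 1.06 to 1.12. Mortality, loss and the pattern of unknown deaths are all assumptions, because the documents give none of them.

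The severity is low. The shifts are small beside intervals such as 0.25 to 3.94, and the outcome is for estimation only. The point is worth acting on because a method that avoids the bias under independent loss can use data the SAP already plans to assemble.

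**What to change.** In SAP 7.4.2:

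1. Define six-month mortality by a fixed day, and say when vital status counts as unascertained.
2. Estimate each arm's risk at that day, and the between-arm difference with a 95% confidence interval, from the time-to-death Kaplan-Meier data planned in SAP 7.4.9. Include all ITT participants.
3. Censor at the last date known alive from contact or chart review, under one written rule applied alike in both arms. The rule should say how deaths found only by later chart review, and reviews showing no death, are dated.
4. Report the number with unknown status by arm.
5. Keep the age-stratified complete-case relative risk alongside as a sensitivity analysis.
6. Label the change post hoc if it is made after data review. SAP 1.2 already requires unplanned analyses to be identified, and the change log for Version 1.4 shows edits made after the primary manuscript was drafted.

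The cost is a few sentences and a last-known-alive date drawn from contacts and chart reviews that are planned anyway. The downside is that Kaplan-Meier assumes that censoring is unrelated to prognosis. If sicker people are lost more often, its estimate is biased too, so the count of unknowns by arm should be shown next to the result.

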7.4.3 Six-month hospitalization

Subjects for whom this outcome cannot be ascertained will be excluded from analysis of this exploratory outcome.

Analysis will be conducted as for the six-month mortality outcome.

7.4.4 Hospitalizations before *DayD1*

For this outcome, the frequency and percentage of ITT subjects who are hospitalized or die on or before the earlier of the day before study drug delivery and *DayR* + 13 will be calculated, overall and by treatment arm.

7.4.5 Quality of life (EQ-5D-5L Assessment)

The EQ-5D-5L quality of life assessment is administered at baseline, 28 days, and 6 months and we will analyze the VAS and an index measure, as described in Section 5.4. Multiple imputation of missing values will be implemented prior to analysis to improve inference given the expectation that missingness may depend on other characteristics. Imputation will include a death indicator for subjects who were known to have died before the assessment was to have occurred. After imputation, differences between day 28 (6 months) and baseline values of the VAS will be calculated. Any subjects whose measurement at day 28 (6 months) is missing because the individual died will then be post-processed to have a value worse than the worst possible difference among survivors (i.e., -101). Mean differences between day 28 (month 6) values and baseline will be compared between arms using a suitable approach (e.g., Van Elteren test), while adjusting for age stratum.

A similar analytical approach will be taken for the EQ-5D-5L index measure, except that the index measure will be set to 0 for individuals who were missing the assessment because they were deceased. No other missing index measure values will be imputed. Note that survivors may have a lower value for this index measure (i.e., <0) than those who are deceased.

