2.1.4 Exploratory Outcome(s)

Exploratory outcomes include, but are not limited to, the following:

- Duration of COVID-19 Symptoms
- Patient-reported instrument measures at baseline, 28 days, and 6 months

- Patient Health Questionnaire 9 (PHQ-9) Total
- Generalized Anxiety Disorder 7-item (GAD 7) Total
- Post-traumatic Stress Disorder Checklist for DSM-5 (PCL-5) Total
- 5-level EuroQol- 5 Dimension (EQ-5D-5L) Visual Analog Scale (VAS) and index measure
- Viral shedding numerical measurements
- Viral shedding at 28 days
- Hospital admissions within 14 days of randomization but prior to day of study drug delivery
- Cumulative mortality at 6 months
- Hospital admission by 6 months

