4. Post-process values that had been imputed during hospitalization by applying LVCF; the value to carry forward is from the most-recent period that (a) has an observed average score AND was earlier in the same hospitalization, if any, or otherwise (b) was the (possibly imputed) assessment period immediately before hospitalization. If there is no previous assessment because the hospitalization was before the baseline assessment, carry forward the imputed baseline value while the hospitalization is ongoing or through the period immediately before a nonmissing average was observed, whichever occurs first.
5. Calculate the average value for $DayA1$ – $DayA15$. If the individual died on or before $DayA15$, average only the values from $DayA1$ to the day before death, inclusive.

The outcome will be modeled with linear regression while adjusting for the baseline average, age group, comorbidity presence, treatment, sex, race, ethnicity, and age group \times comorbidity interaction effects. Rubin's rules will be used to make final inference, with interest on the two-sided p-value for the treatment effect, which will be declared statistically significant if < 0.05 .

As with the imputation model, the main analysis model for the average symptom level will be restricted to ITT subjects who had at least one observed symptom average from among the baseline or $DayA1$ – $DayA15$ measurements.

7.3.3 Persistence of Viral Shedding on Day 28

This analysis will omit subjects known to have died on or before $DayR + 30$ without having a Day 28 swab result. (The Day 28 swab may be in a ± 2 day window, so a participant may

have a “Day 28” swab even if the subject died on *DayD28*.) Some missing data will be assumed positive or negative, as described for this day 28 shedding outcome in Section 5.4. Then, multiple imputation will be employed for subjects with still-missing values for the Day 28 viral shedding outcome. There will be a minimum of $m = 10$ imputed datasets, and variables used to impute the outcome will include variables such as prior hospitalizations while on study, treatment arm (if imputation is not already stratified by treatment arm), age group, and viral shedding history.

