7.4.6 Six-month depression (PHQ-9 Total)

Analysis of the PHQ-9 Total will be conducted in the manner analogous to that of the 28-day and six-month EQ-5D-5L VAS.

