7.4.7 Six-month anxiety (GAD-7 Total)

Analysis of the GAD-7 Total will be conducted in the manner analogous to that of the 28-day and six-month EQ-5D-5L VAS.

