7.4.8 Post-traumatic stress disorder (PCL-5 Total)

Analysis of the PCL-5 Total will be conducted in the manner analogous to that of the 28-day and six-month EQ-5D-5L VAS.

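### Five exploratory patient-reported outcomes are compared as change from baseline with age as the only adjustment, which loses precision unless the baseline-to-follow-up slope is 1

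*SAP*

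**What the plan says.** SAP 2.1.4 lists "Patient-reported instrument measures at baseline, 28 days, and 6 months" among the exploratory outcomes, so a baseline score is collected for every instrument.

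For the EQ-5D-5L VAS, SAP 7.4.5 imputes missing values and forms the difference between follow-up and baseline. It sets that difference to -101 for participants who died, and then specifies: "Mean differences between day 28 (month 6) values and baseline will be compared between arms using a suitable approach (e.g., Van Elteren test". The adjustment is given as "while adjusting for age stratum" and nothing more.

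For the index, "A similar analytical approach will be taken for the EQ-5D-5L index measure", except that death takes the value 0 and no other missing index value is imputed.

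The other three instruments follow the VAS:
- SAP 7.4.6: "Analysis of the PHQ-9 Total will be conducted in the manner analogous to that of the" VAS.
- SAP 7.4.7: "Analysis of the GAD-7 Total will be conducted in the manner analogous to that of the" VAS.
- SAP 7.4.8: "Analysis of the PCL-5 Total will be conducted in the manner analogous to that of the" VAS.

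That makes five outcomes at two time points. For the daily symptom average, a secondary outcome, SAP 7.3.2 does use the baseline score as a covariate: "The outcome will be modeled with linear regression while adjusting for the baseline average".

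**The concern.** Subtracting baseline gives it a fixed weight of 1. The efficient weight is the slope of follow-up on baseline, which is the correlation times the ratio of follow-up SD to baseline SD. Where the slope is below 1, subtraction adds baseline noise that a covariate would not. The baseline survey is taken between randomization and drug delivery (SAP 5.4), soon after a positive test, and follow-up comes 28 days or 6 months later. A slope below 1 is therefore plausible, at least for the VAS, but the documents do not state one.

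What is at stake is the chance of detecting a real later difference in quality of life, depression, anxiety or post-traumatic stress, using data the trial already holds.

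There is also a point of wording. The sentence speaks of mean differences, but its example test compares ranks. A mean that includes deaths coded -101, 28, 22 or 81 on the change scale has no clear meaning, although those codes work properly as worst ranks.

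**Working it through.** **The plan's own figure.** The documents give no power or sample size for these outcomes. Protocol Table 2 concerns the primary outcome only, and it reproduces. The hazard ratio is exp(2(1.960 + 0.842)/sqrt(400 × rate)). At a rate of 50% this is exp(5.603/sqrt(200)) = 1.486, against 1.49 in the table. The remaining rows come to 1.459, 1.436, 1.416, 1.398, 1.382 and 1.368, against 1.46, 1.44, 1.42, 1.40, 1.38 and 1.37. The table has no bearing on this point.

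**Inputs.** From the documents: 200 per arm (protocol 2.7), and change as the compared quantity with age stratum as the only adjustment (SAP 7.4.5). Assumed, because the documents are silent: correlation rho between baseline and follow-up, SD ratio k (follow-up/baseline), two-sided alpha of 0.05 for these outcomes, and no missing data.

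**Variances**, in units of the baseline variance:
- Change: 1 + k² − 2·rho·k
- Baseline-adjusted: k²(1 − rho²)
- Difference: (1 − rho·k)²

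The difference is never negative and is zero only when the slope rho·k equals 1. This fixes the direction whatever the unknown values are.

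**Equal SDs (k = 1).** The adjusted variance divided by the change variance is (1 − rho²)/(2(1 − rho)) = (1 + rho)/2. When the adjusted analysis has 80% power, the change score has power Φ(2.802·sqrt((1 + rho)/2) − 1.960). At rho 0.3 this is Φ(2.802 × 0.806 − 1.960) = Φ(0.299) = 62%. The smallest difference detectable with 80% power is 2.802·sqrt(variance)·sqrt(2/200).

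| rho | Var change | Var adjusted | Change/adjusted | Adjusted N matching 400 on change | Power of change when adjusted has 80% | Detectable difference in SD, change → adjusted |
|---|---|---|---|---|---|---|
| 0.3 | 1.40 | 0.91 | 1.54 | 260 | 62% | 0.331 → 0.267 |
| 0.5 | 1.00 | 0.75 | 1.33 | 300 | 68% | 0.280 → 0.243 |
| 0.7 | 0.60 | 0.51 | 1.18 | 340 | 73% | 0.217 → 0.200 |
| 0.8 | 0.40 | 0.36 | 1.11 | 360 | 76% | 0.177 → 0.168 |
| 0.9 | 0.20 | 0.19 | 1.05 | 380 | 78% | 0.125 → 0.122 |

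Below rho 0.5 the change score is less precise than the follow-up score with no baseline at all, because 2(1 − rho) exceeds 1.

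**Unequal SDs.** At rho 0.3, 0.5 and 0.7 the adjusted/change variance ratio is 0.42, 0.47 and 0.49 for k = 0.7, and 0.81, 0.91 and 0.99 for k = 1.3.

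**Rank methods.** Because the named test is rank-based, the direction was also checked by simulation. Scores were normal, with 400 participants, four assumed age strata, 0.5% deaths ranked worst and 3,000 trials per setting. The effect was the one at which change has 80% power in theory. The Van Elteren test on change gave 76%, 77% and 78% power at rho 0.3, 0.5 and 0.7. The same test on follow-up ranks adjusted for baseline rank and stratum gave 92%, 86% and 81%. With no effect, both rejected in 4.5% to 5.8% of trials.

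**How far scenarios differ.** With 300 participants, 1% deaths, a 0.3 SD effect and rho 0.7, change versus adjusted gave:
- 89% versus 89% for normal scores;
- 79% versus 88% for an assumed skewed PHQ-9-like score;
- 41% versus 86% when that score also had an assumed 0.7 SD average recovery.

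The loss at one correlation thus runs from 0 to 45 points, depending on features the documents do not give.

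**The case against.** The strongest reply is that these outcomes are exploratory. They have no power target or stated alpha, and SAP 5.3 applies no multiplicity adjustment. A fuller model for a secondary outcome in SAP 7.3.2 and a simple stratified rank test here can be defended as a gradation. This stands: a reader might infer an internal contradiction from the comparison with 7.3.2, and the documents do not support that. The comparison shows only that baseline adjustment is within the plan's normal practice.

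A reader might also infer that the planned comparison is biased or invalid. It is not. Change is unbiased under randomization and type I error holds. The death codes lie beyond any survivor's change, so under a rank test they simply place deaths last.

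A reader might infer a large expected loss from simulations of skewed scores. The scenario range in the working rules that out. Nor do the documents establish that the slope is far below 1 for the depression, anxiety and post-traumatic stress scores.

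The wording of SAP 7.4.5 does leave the test open, and a baseline-adjusted rank method on change is not excluded. But the compared quantity is fixed as change and age is the only adjustment named, so the open wording does not supply the missing term.

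Finally, the change is not free of timing problems. The change log for SAP Version 1.4 places its discussions after the primary manuscript was drafted and refers to results already seen. It does not say whether these five outcomes were among them. This stands, and it shapes the fix.

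**Conclusion.** The point holds as a loss of precision on five exploratory outcomes. The direction is certain: the planned comparison is less precise than a baseline-adjusted one unless the slope is exactly 1. The size is not known. Under equal SDs the planned comparison gives up 18, 12 and 7 points of power at rho 0.3, 0.5 and 0.7 relative to an adjusted analysis with 80%, and about 4 points or fewer from rho 0.8 upward. The loss is larger if scores spread less at follow-up than at baseline, and smaller if they spread more (over the rho range 0.3 to 0.7). These figures rest on assumed correlations and SD ratios, and the powers also on complete data.

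Separately, the SAP should not describe a rank test as a comparison of means. The change is worth making because the baseline score is already in hand, but the primary and secondary analyses do not depend on it.

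**What to change.** In SAP 7.4.5 to 7.4.8:
- Analyse the 28-day and 6-month scores themselves, with the baseline score as covariate and age group as stratum, for example by rank ANCOVA or proportional-odds regression.
- For the VAS, PHQ-9, GAD-7 and PCL-5, rank deaths one step beyond the worst possible follow-up score. From the ranges in SAP 5.4 these codes are -1, 28, 22 and 81. Pool over the imputations, using a statistic that is approximately normal under the null, as SAP 7.3.3 already requires for its own test.
- For the index, keep the value 0 for deaths and apply the same baseline adjustment to observed values. No Rubin pooling is needed, because other missing index values are not imputed.
- Describe the Van Elteren test as a rank comparison.
- State that the baseline survey may fall between randomization and drug delivery. This affects the change score equally.

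If these outcomes have already been analysed, keep the planned comparison and add the adjusted one as a supplementary analysis, identified as post hoc as SAP 1.2 requires.

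The cost is SAP wording, some extra programming (with the dual programming of SAP 5.5 where it applies) and the labelling. No new data are needed.
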